#### *9.1.1.3 Questionnaire on Pain caused by Spasticity (QPS)*

The QPS is a patient-reported outcome for children and adolescents (2-17 years) with CP on spasticity-related pain. A self-report version for the children/adolescent, an interview-version for the children/adolescent, and a proxy-report version for the parent(s)/caregiver are available for both UL and LL spasticity-related pain assessment. For this study, in addition to the UL versions that will be used for all subjects/parents/caregivers the LL versions will also be used for subjects with treatment combinations including UL and LL

treatment. While pain intensity is reported by the children/adolescents, pain frequency (based on observed pain behaviors) will be documented by the parent(s)/caregivers. Thus, the information provided by the children/adolescents complements the one of the parents/caregivers. Pain intensity and frequency of the QPS are assessed for general pain and for four different activity situations. The situations are described in different questions for rest, normal day activities, physical exercise and for an individually defined ‘very hard thing to do’.

The parent/caregiver version of the QPS should be always completed and always (if possible) from the same parent/caregiver throughout the study. Caregiver(s) may substitute parent(s) for the assessment of QPS, if they are main social contacts of subjects, e.g. in a special-care home. Based on the cognitive, communicative, and motor abilities of a subject, the QPS will be self-administered by the subject or the interview version will be used by the site staff. If no assessment by the subject is possible due to age or cognitive impairments, only the parent(s)/caregiver will complete their instrument version.

The assessment of spasticity associated pain by the subject or parent(s)/caregiver will be done at all personal visits in MP [REDACTED]. Only the QPS versions applicable for the chosen treatment combination (A-E) will be utilized (i.e. UL or UL and LL). The different final versions of the questionnaire are displayed in [Appendix 16.6](#).

[REDACTED]

[REDACTED]

[REDACTED]

[REDACTED]

[REDACTED]

[REDACTED]

[REDACTED]

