- Change from baseline in scores of pain intensity (from subjects) and pain frequency (from parent/caregiver) assessed with ‘Questionnaire on Pain caused by Spasticity (QPS)’ to all post baseline visits of MP (V3, V4, and V5). In the definition of this variable the visit numbers were added.

The QPS is a patient-reported outcome for children and adolescents (2-17 years) with CP on spasticity-related pain. For this study, in addition to the UL versions that will be used for all subjects/parents/caregivers, the LL versions will also be used for subjects with treatment combinations including UL and LL treatment. While pain intensity is reported by the children/adolescents, pain frequency (based on observed pain behaviors) will be documented by the parent(s)/caregiver(s). In addition, parent(s)/caregiver(s) report on pain location and observed pain behaviors. Thus, the information provided by the children/adolescents complements the one of the parents/caregivers. Pain intensity and frequency of the QPS are assessed for general pain and for four different activity situations. The situations are described in different questions for rest, normal day activities, physical exercise and for an individually defined ‘very hard thing to do’. First it is always asked if spasticity-related pain for each activity situation occurred (Yes/No) and then how severe the experienced spasticity was (6-point rating scale) or how frequent pain behavior was observed (5-point rating scale).

From the self-administered version and from the interviewer-administered version of the QPS the QPS child/adolescent score will be calculated as sum of the activity related pain items No. 5, 7, 9, and 12 divided by 4. In case one or more of the 4 items are missing the corresponding QPS score will not be calculated. The item No. 3 of the self-administered version and the interviewer-administered version will be not included into this score, but will be assessed separately as child/adolescent general pain intensity item.

From the parent/caregiver version the QPS parent/caregiver score will be calculated as sum of the items No. 9b, 10b, 11b, and 13b divided by 4. In case one or more of the 4 items are missing the corresponding QPS score will not be calculated. The item No. 8 of the parent/caregiver version will be not included into this score, but will be assessed separately as parent/caregiver general pain frequency item.

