The difference between treatment groups in the change from baseline in AS score for each treated clinical pattern (e.g., flexed elbow, flexed wrist, flexed fingers) of the UL at all other post-baseline visits will be analyzed by a mixed model repeated measurement analysis as described for the primary efficacy variable. Furthermore, descriptive summary statistics, shift tables and frequency tables of changes will be given. Besides the model based missing value imputation approach, a mixed model without repeated measures will be applied with missing values imputed by LOCF and observed case analyses.

Questionnaire on Pain caused by Spasticity

All analyses regarding the QPS will be performed separately for upper limbs and for lower limbs. The QPS child/adolescent score, the child/adolescent general pain intensity item, the QPS parent/caregiver score, and the parent/caregiver general pain frequency item will be analyzed by using descriptive summary statistics at all visits and for changes from baseline to all post-baseline visits. The child/adolescent general pain intensity item and the parent/caregiver general pain frequency item will additionally be analyzed by using frequency tables. All other single items of the QPS will be listed.

The QPS child/adolescent score and the QPS parent/caregiver score will be analyzed by an ANCOVA. The dependent variable is defined as the change from baseline in the QPS score. The independent variables are defined as treatment group (high dose and in 2nd step mid dose vs. low dose), pooled sites, BoNT-A pre-treatment status (pre-treated, treatment naïve) as fixed factors and the covariates are the QPS score at baseline (Day 1 of MP) and the GMFCS-E&R level at Screening Visit. LOCF as well as observed case analyses will be performed.

In these frequency tables of the child/adolescent general pain intensity item and descriptive summary statistics of the QPS child/adolescent score and the child/adolescent general pain intensity item and the ANCOVA of the QPS child/adolescent score, subgroup analyses will be done for the self-administered version and for the interviewer-administered version in addition to the pooled analysis. LOCF for the QPS child/adolescent score and the child/adolescent general pain intensity item will only be applied for the pooled version if both versions (self-administered and interviewer-administered) are missing. For the self-administered and interviewer-administered version no LOCF will be performed.

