Not all children and adolescents are able to make the QPS assessment self-administered or interviewer-administered version at all visits, which will presumably lead to a high number of missing values for the QPS child/adolescent score and the child/adolescent general pain intensity item. For this reason observed case analyses of QPS child/adolescent score and child/adolescent general pain intensity item is of main interest and the LOCF analysis is only a sensitivity analysis, which must be interpreted with caution.

Global Impression of Change Scales

Child's/Adolescent's (if applicable) and Parent's/Caregiver's GICS for upper limb at Day 29 (Week 4) will be analyzed descriptively by an ANCOVA model as described for the co-primary efficacy analysis. Furthermore, frequency tables, Wilcoxon rank-sum tests and descriptive summary will be performed. Missing values will be replaced by "0" (no change) as for the co-primary efficacy variable and an observed case analyses will be performed. Not all children and adolescents are able to make the GICS assessment, which will presumably lead to a high number of missing values for the Child's/Adolescent's GICS. For this reason observed case analyses of Child's/Adolescent's GICS is of main interest and the worst case analysis is only a sensitivity analysis, which must be interpreted with caution.

[REDACTED]

[REDACTED]

[REDACTED]

[REDACTED]

[REDACTED]

[REDACTED]

[REDACTED]

[REDACTED]

[REDACTED]

[REDACTED]

[REDACTED]

[REDACTED]

[REDACTED]

[REDACTED]

[REDACTED]

[REDACTED]

[REDACTED]

[REDACTED]

[REDACTED]

[REDACTED]

[REDACTED]

[REDACTED]

[REDACTED]

[REDACTED]

[REDACTED]

[REDACTED]

[REDACTED]

[REDACTED]

[REDACTED]

[REDACTED]

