7.7 Special Statistical/Analytical Issues

7.7.1 Discontinuations and Missing Data

Discontinued subjects will not be replaced.

The primary and secondary efficacy variables of the Ashworth scale score will be analyzed on the FAS and PPS of the MP using MMRM for accounting for missing data. The model will be based on the observed cases data without imputing missing values. As sensitivity analysis for the primary efficacy variable and for the secondary efficacy variables of the AS score an ANCOVA model without repeated measures will be applied. The LOCF principle will be followed on the FAS and PPS of the MP, i.e., the last observation (including baseline) will be carried forward to Week 4 and all further visits with missing values. In addition, further sensitivity analysis for the primary and secondary efficacy variables, the so called observed case analysis without missing data replacement, will be performed on the FAS and PPS of the MP to explore the impact of the respective missing imputation principle.

In case of missing data in the co-primary variable these will be imputed by “0” (no change). Assuming a similar percentage of missing data in all three treatment arms this imputation

leads to a decreased difference of the treatment effects. For this reason the “no change” imputation is considered as conservative approach.

As the GICS is only measured at Control Visit V3, it is not possible to apply a model based analysis like mixed model repeated measurement. Therefore, only ‘no change replacement’ and observed case analysis as sensitivity analysis will be performed.

For the secondary efficacy variable ‘Questionnaire on Pain caused by Spasticity’ LOCF and observed case analyses will be performed on the FAS and the PPS. For the secondary efficacy variable ‘Global Impression of Change Scales’ missing values will be replaced by “0” (no change) and an observed case analyses will be performed on the FAS and the PPS.

For child’s/adolescent’s GICS and QPS the observed case analysis is the main analysis of interest, and the ‘no change replacement’ (GICS) and the LOCF (QPS) are the respective sensitivity analyses.

Missing assessments except for primary or co-primary efficacy variable will not be listed as protocol deviations.

Observed case analysis will be performed for all efficacy data of the OLEX period, i.e. missing data of the OLEX will not be replaced.

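### The QPS pain scores are measured at three visits but analysed only by an ANCOVA without a visit term; an MMRM over V3 to V5, as used for the Ashworth scores, would make better use of intermittently missing child scores

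*SAP*

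**What the plan says.** SAP 6.1.2 defines the QPS variable as change from baseline "to all post baseline visits of MP (V3, V4, and V5", so there are three post-baseline measurements. The same section voids a score at a visit if any one of its four items is missing.

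SAP 7.1.2 then states: "The QPS child/adolescent score and the QPS parent/caregiver score will be analyzed by an ANCOVA". The listed terms are treatment, pooled site, BoNT-A pre-treatment status, baseline QPS and GMFCS level. No visit term, visit-by-treatment term or repeated factor is listed, and the visit or visits at which the ANCOVA is run are not given. On missing data it says "LOCF as well as observed case analyses will be performed", and SAP 7.7.1 repeats "LOCF and observed case analyses will be performed on the FAS and the PPS".

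For child self-report, SAP 7.1.2 notes that not every child can do the assessment at every visit, "which will presumably lead to a high number of missing values for the QPS child/adolescent score and the child/adolescent general pain intensity item". It therefore makes observed cases the analysis of main interest for the child/adolescent score and treats LOCF as a sensitivity analysis to be read cautiously. For the parent/caregiver score it does not say which of the two is the main analysis.

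In the same section, the secondary Ashworth changes "will be analyzed by a mixed model repeated measurement analysis as described for the primary efficacy variable". SAP 7.1.2 and 7.7.1 explain why the GICS gets no MMRM: it is assessed only at V3. No reason is given for the QPS.

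**The concern.** The QPS has the repeated structure for which the SAP already has a model and code, and the SAP expects many gaps in one of its two scores. An observed-case ANCOVA at a given visit leaves out any child without a score at that visit, even when the same child has scores at the other visits. The correlation between visits goes unused.

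The missing-data assumption is also stronger. The ANCOVA is valid if missingness depends only on the covariates in its model. An MMRM also allows missingness to depend on QPS scores observed at other visits.

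The alternative offered is weak. The QPS is collected at site visits, and only a telephone contact falls between V2 and V3. LOCF at V3 is therefore baseline carried forward, that is, zero change in pain. SAP 7.1.1 acknowledges the same equivalence for the Ashworth score.

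At stake are the precision, and under some missingness mechanisms the bias, of the exploratory dose comparison on pain.

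**Working it through.** **The plan's own figures.** The documents give no power, SD, between-visit correlation or missing rate for the QPS, so no QPS figure can be reproduced. The Ashworth sizing in SAP section 4 does reproduce. With a difference of 0.30, SD 0.6 and 172 versus 86 subjects, the noncentrality is 0.30 / (0.6 × √(1/172 + 1/86)) = 3.79. A two-sided t-test at 0.05 then has 96.5% power, as stated. This does not depend on how the QPS is analysed.

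**Inputs for the comparison.** From the documents: three post-baseline visits, and 172 versus 86 subjects for high versus low dose. Assumed, because the documents are silent: residual correlation ρ between any two visits (0.3 to 0.7), share m of assessable children with a gap at the visit (10-30%), and an effect of 0.4 SD for the power illustration.

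**Formula.** If gaps are completely at random and the other two visits are observed, the variance of the treatment difference at one visit, MMRM relative to observed cases, is about 1 − m × R². Here R² = 2ρ²/(1 + ρ) is the share of variance explained by the other two visits.

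- ρ = 0.3: R² = 0.18/1.3 = 0.138
- ρ = 0.5: R² = 0.50/1.5 = 0.333
- ρ = 0.7: R² = 0.98/1.7 = 0.576

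| Gap share m | ρ = 0.3 | ρ = 0.5 | ρ = 0.7 |
|---|---|---|---|
| 10% | 0.986 | 0.967 | 0.942 |
| 20% | 0.972 | 0.933 | 0.885 |
| 30% | 0.958 | 0.900 | 0.827 |

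For ρ of 0.5 to 0.7 the reduction runs from 1 − 0.967 = 3% to 1 − 0.827 = 17%. At ρ = 0.3 it is 1-4%.

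**Simulation check.** Settings were 172 versus 86 subjects, three visits, equal correlation, known covariance, no baseline covariate, 40% of children never assessable, and 20% random gaps per visit among the rest. About 124 children contribute at a visit under observed cases and about 154 under an MMRM. The variance ratio was 0.93 (ρ = 0.5) and 0.89 (ρ = 0.7). Power for 0.4 SD rose from 55% to 58% and from 57% to 60%.

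**Where there is no gain.** With 40% never assessable and no intermittent gaps, the simulated ratio is exactly 1.00. With 3% gaps and nobody unassessable, it is 0.98-0.99. The 3% is the rate SAP section 4 uses at the primary time point, borrowed here for a nearly complete parent/caregiver score.

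**Bias.** Simulations in which missingness at V4 and V5 depended on the V3 score show that observed cases can mislead while the MMRM stays near the truth. Where 24-33% were missing and the true effect was −0.40 SD, observed cases gave −0.35 to −0.37 at V4 and the MMRM −0.39 to −0.41. In a deliberately extreme case, with the dependence running in opposite directions in the two arms and a true effect of 0.40, observed cases gave 0.79 and the MMRM 0.40. These mechanisms are assumed.

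**The case against.** The strongest objection is the cause of the missing data. Protocol 9.1.1.3 says: "If no assessment by the subject is possible due to age or cognitive impairments, only the parent(s)/caregiver will complete their instrument version". A child who can never respond has no baseline and no follow-up score, and an MMRM recovers nothing. This stands for those children, and their share is unknown. It does not cover everyone. The SAP's forecast refers to ability at all visits, whereas the matching sentence for the single-visit GICS has no such reference. The item rule in SAP 6.1.2 can void a single visit. And LOCF on the pooled child version can act only where an earlier score exists. Some intermittent gaps are therefore expected.

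Three further objections stand:

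- The forecast of many missing values concerns child report only. The protocol asks for the parent/caregiver version every time, so the gain there is likely to be small.
- QPS tests are exploratory, and protocol 12.4.1.2 planned only frequency tables and summary statistics. The SAP's ANCOVA already goes beyond that.
- Dropping LOCF would leave unmet the statement in protocol 12.4.7.1 that missing main-period data of the other secondary variables will be replaced by a method given in the SAP.

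A reader might infer more than the documents support:

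- That collected pain data are discarded. They are not: QPS scores are summarised descriptively at all visits, and in a visit-wise ANCOVA each score enters its own visit's analysis. What goes unused is information across visits.
- That the SAP prescribes a separate ANCOVA for each visit. That is the natural reading, but it is not written.
- That the planned analysis is biased. This requires missingness to depend on pain at another post-baseline visit, and the only cause the documents name is ability.

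**Conclusion.** The point holds as an inexpensive improvement to an exploratory secondary endpoint. The QPS has three post-baseline visits, its planned model has no visit or repeated term, the Ashworth scores get an MMRM, and the one reason given against an MMRM does not fit. For a child with a score at some visits only, the planned main analysis ignores the other scores at the missed visit and rests on a stronger missing-data assumption.

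The size is modest: about 3-17% lower variance at a visit, for assumed intermittent gaps of 10-30% and correlation of 0.5-0.7. This rests on gaps at random, the other visits being observed, and a model that lets effects differ by visit. It is zero for children who can never complete the QPS and about 1-2% for a score with 3% gaps. Type I error control, the sample size and the confirmatory hierarchy are unaffected.

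**What to change.** In SAP 7.1.2 and 7.7.1, make an MMRM of change from baseline over V3, V4 and V5 the main analysis of the child/adolescent and parent/caregiver QPS scores, separately for upper and lower limb as already planned.

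- **Model:** treatment, pooled site, pre-treatment status, baseline QPS, GMFCS level, visit and visit-by-treatment, with visit as repeated factor. The code in SAP 7.1.1 can be reused. Preferably add baseline-by-visit, which that code lacks, so that the baseline effect may differ by visit.
- **Reporting:** give the treatment difference at each of V3, V4 and V5. This also settles which visits are analysed and which analysis is the main one for the parent/caregiver score.
- **Covariance:** unstructured, with a fallback structure stated in advance.
- **Sensitivity analyses:** keep the observed-case ANCOVA, naming its visits, and keep LOCF so that protocol 12.4.7.1 is met.
- **Disclosure:** tabulate how many children have QPS scores at none, some and all visits, by arm, so that the reader can see how much the MMRM could recover.

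The cost is SAP wording and reuse of an existing model before unblinding, with no new data. The downside is that the unstructured covariance may not converge in the smaller child-report set, hence the fallback.

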7.2 Pharmacodynamic Variables

Not applicable.

7.3 Pharmacokinetic Variables

Not applicable.

7.4 Pharmacogenetic Variables

Not applicable.

7.5 Safety Variables

All safety analyses of the MP will be performed on the SES of the MP. All safety analyses of the OLEX Period will be performed on the SES of the OLEX period. Analyses will be based on both, total population and by Main Period treatment group (high, mid, low). For this purpose the Main Period treatment group as treated instead of as randomized will be used. In the unlikely case that a subject has received mid or low dose instead of the planned high dose during the OLEX Period, he/she will be analyzed in total group of the OLEX tables together with all other subjects with the correct high dose treatment.

For safety variables the last measurement before start of treatment is defined as baseline value.

7.5.1 Primary Safety Variable

Not applicable.

7.5.2 Secondary Safety Variables

Adverse events

AEs will be coded according to the Medical Dictionary for Regulatory Activities (MedDRA, version 21.0). For MP, only treatment emergent adverse events (TEAEs) of the MP will be analyzed, which are defined as AEs with onset or worsening on or after date and time of the first MP administration and before date and time of the first OLEX administration at V6. For subjects who do not receive an OLEX administration all AEs with onset or worsening on or after date and time of the first MP administration will be considered as TEAEs of MP. TEAEs of the OLEX are defined as AEs with onset or worsening at or after date and time of the first OLEX administration at V6. TEAEs will be allocated to an injection cycle x in the OLEX Period, if adverse events has onset or worsening on or after injection x and before injection x+1 (if applicable). TEAEs of the OLEX will be analyzed in total and per treatment cycle. Additionally TEAEs of the MP and the OLEX period will be displayed together in total.

Only TEAEs will be analyzed. Non-TEAEs will only be listed.

If an AE worsens between start and end of this AE it will be considered as new AE starting with the date of the worsening. In this case the imputation of end dates within episodes of the

same AE will be done by setting the end date/end time to start date/start time of the consecutive worsening record.

In detail missing or partially missing start and stop dates of an AE will be imputed as follows for the calculation of the duration of an AE:

- if start time is missing and start date is given and not equal to date of an injection visit, set start time to 00:00, else if start date is equal to date of an injection visit set start time to time of injection, if given (else 00:00)
- if start date/time is completely missing and end date is before first exposure in the MP: no imputation
- if start date/time is (partially) missing and end date after or equal first exposure in the MP or missing:
 - only start day is missing, but start month and start year same as an injection visit: set start day and start time to day and time of this injection visit, else set start day to 1 and start time to 00:00
 - start day and start month are missing, but start year is the same as year of first exposure in the MP: set start day, start month, start time to day, month, time of first exposure in the MP, else set start day and start month to 1 and start time to 00:00
 - start date/time completely missing and end date/time not before date/time of first exposure in the MP, set start date/time to date/time of first exposure in the MP
 - if AE end date and time are missing set end date to study end date (i.e. last contact or last visit of the study) and end time to 23:59
 - if AE end date/time is partially missing, set end day to last day of the given month or end day/month to 31/12 of the given end year and missing end time to 23:59
 - if AE end time is missing set time to 23:59.

Imputation rules for multiple records in case of AE worsening:

- For missing AE start date/time the imputation strategies as defined above will be applied to all records of the same AE.
- For missing TEAE end date/time the imputation strategies as defined above will be applied to the last record of the same TEAE.

Calculation of time to onset/duration of AEs [days]:

- Time to onset of an AE is defined as start date of AE - date of most recent administration of study drug [+ 1 for AE starting after start of treatment]
- The duration will be calculated as stop date - onset date + 1 for each episode of worsening.

Incidences will be calculated for TEAEs overall (MP+OLEX), overall OLEX and by injection cycle on the system organ class (SOC) level and on the preferred term (PT) level (i.e., total, by worst intensity, by worst relationship, and by worst outcome). Listings and, if applicable, tables displaying incidences for TEAEs leading to discontinuation, serious TEAEs, related serious TEAEs, TEAEs of special interest, and deaths will also be provided. Additionally the number and percentage of subjects with at least one non-serious TEAE with incidence $\geq 5\%$

in any MP treatment group or in the OLEX Period and number of non-serious TEAE will be displayed by SOC level and PT level. Time to onset and duration of AEs will be listed. Time to onset and duration of AEs will be listed.

For any missing data of adverse events, a worst case strategy will be applied for all analysis tables. The intensity will be imputed by the worst intensity “severe”, the causal relationship will be imputed by the worst relationship “drug related”. Missing data of the worst outcome will be imputed by “unknown”. If a subject has more than one outcome within a preferred term (PT) only the worst outcome will be used in the frequency tables. Also on subject level only the worst outcome category per subject will be counted in the frequency table. The worst outcome is defined in the following order:

- recovered/resolved
- recovered/resolved with sequelae
- recovering/resolving
- not recovered/not resolved
- unknown
- fatal

TEAESIs are defined as TEAEs that are thought to possibly indicate toxin spread. A list of adverse events of special interest possibly indicating toxin spread is given in **Table 1: List of Adverse Events of Special Interest Possibly Indicating Toxin Spread.**

Table 1: List of Adverse Events of Special Interest Possibly Indicating Toxin Spread

MedDRA PT	MedDRA PT
Accommodation disorder	IIIrd nerve paresis
Areflexia	Ileus paralytic
Aspiration	IVth nerve paresis
Botulism	Monoparesis
Bradycardia	Muscular weakness
Bulbar palsy	Paralysis
Constipation	Paraparesis
Cranial nerve palsies multiple	Paresis
Cranial nerve paralysis	Paresis cranial nerve
Diaphragmatic paralysis	Peripheral nerve palsy
Diplopia	Peripheral paralysis
Dry mouth	Pelvic floor muscle weakness
Dysarthria	Pneumonia aspiration
Dysphagia	Pupillary reflex impaired
Dysphonia	Quadriparesis
Dyspnoea	Respiratory arrest
Extraocular muscle paresis	Respiratory depression
Eyelid function disorder	Respiratory failure
Eyelid ptosis	Speech disorder
Facial paralysis	Trigeminal nerve paresis
Facial paresis	Urinary retention
Hemiparesis	Vision blurred
Hypoglossal nerve paresis	Vocal cord paralysis
Hyporeflexia	Vocal cord paresis
Hypotonia	
Wording of PTs is according to MedDRA version 21.0	

To fulfill FDA requirements, TEAE data will be screened for suicidal events. The MedDRA PTs of all TEAEs will be checked using standard MedDRA query (SMQ) „Suicide/self-injury“. Resulting TEAE findings will be listed in a separate listing. A list of the MedDRA PTs of the SMQ „Suicide/self-injury is given in Table 2.

Table 2: List of Adverse Events of Standard MedDRA Query „Suicide/self-injury“

MedDRA PT:	MedDRA PT:
Columbia suicide severity rating scale abnormal	Self injurious behaviour
Completed suicide	Self-injurious ideation
Depression suicidal	Suicidal behaviour
Intentional overdose	Suicidal ideation
Intentional self-injury	Suicide attempt
Poisoning deliberate	Suicide threat

In addition all comment fields of the case report form (CRF) and all investigator reported terms of TEAEs will be screened for the following terms or term elements (‘strings’) and listed in a separate listing:

Table 3: List of Search Terms and Search Strings of Possibly Suicidal Events

Term:	Term:
attempt	self inflict
cut	self injur
gas	self-damage
hang	self-harm
hung	self-inflict
jump	self-injur
mutilate	shoot
overdos	slash
self damage	suic
self harm	

Obvious false positive findings will be excluded from the listing (e.g., “gas” in “gastrointestinal” or “cut” in “acute” or in “cutaneous”).

